9.2.3 Study Visits

9.2.4 Study Discontinuation

Boehringer Ingelheim reserves the right to discontinue the study overall or at any time for the following reasons:

- In the overall population, Stiolto initiators from September 2017 March 2020 will be matched using Propensity Score Matching (PSM) with Trelegy initiators from September 2017 – March 2020 on a prespecified list of covariates listed in section 10.2.2. to ensure that the two cohorts are well balanced (i.e., standardized difference ≤10%) across all characteristics. However, for any baseline characteristics with significant differences (Standardized differences (SD) greater than 0.10 (10%)) after PSM matching, these characteristics will be included as covariates in the regression models, or we will develop interaction terms to match on or discontinue the study if major channeling (SD>10%) is observed.
- 2. Violation of Good Pharmacoepidemiology Practice (GPP), the study protocol, or the contract by a research collaborator, disturbing the appropriate conduct of the study

The research collaborator will be reimbursed for reasonable expenses incurred in case of study termination (except in case of the second reason).

9.3 VARIABLES

The definitions for exacerbations are as below.

- A severe exacerbation will be defined as follows:
 - An inpatient admission or an ER visit with a COPD diagnosis code in the primary position; or
 - An inpatient admission or an ER visit with a diagnosis code for acute respiratory failure in the primary position and a COPD diagnosis code in any position; or
 - An inpatient admission or an ER visit with a diagnosis code for acute respiratory failure in the primary position + an inpatient admission or an ER visit within ±7 days with a COPD diagnosis code in any position.
- A moderate exacerbation will be defined as follows:
 - An ambulatory (office or outpatient) visits with a COPD diagnosis code in any position + a pharmacy claim for an oral corticosteroid (OCS) prescription within ±7 days of the office/outpatient visit; or

Proprietary confidential information © 2022 Boehringer Ingelheim International GmbH or one or more of its affiliated companies

- \circ An office or outpatient visit with a COPD diagnosis code in any position + a pharmacy claim for respiratory antibiotic prescription within ±7 days of the office/outpatient visit; or
- An office or outpatient visit with a COPD diagnosis code in any position + a pharmacy claim for an OCS + a pharmacy claim for respiratory antibiotic prescription within ±7 days of the office/outpatient visit.
- Pneumonia diagnosis: Binary indicators will be created to identify patients with a diagnosis of 1) pneumonia (Appendix 1). The time to first pneumonia diagnosis, and time to first pneumonia, during follow-up will also be captured.
- Pneumonia-related hospitalization: Binary indicators will be created to identify
 patients with an acute hospitalization with diagnosis of 1) pneumonia in any
 position (Appendix 1) The time to first pneumonia-related hospitalization during
 follow-up will also be captured.
- COPD exacerbation and/or pneumonia diagnosis: Binary indicators will be created to identify patients with each of the following composite outcomes: severe COPD exacerbation or an acute hospitalization with a diagnosis of pneumonia in any position, severe COPD exacerbation or a hospitalization with a diagnosis of pneumonia in any position, any COPD exacerbation or pneumonia diagnosis in any position, and any COPD exacerbation or pneumonia diagnosis in any position. Time to event variables will be created for each composite outcome during the follow-up period.

The following outcomes will be measured in the baseline and follow-up periods. The baseline period will include claims occurring on the index date, except for the index medication claims, which will be included in the follow-up period.

- All-cause health care resource utilization: Indicator variables and counts of physician office visits, hospital outpatient visits, ED visits, "other" (non-inpatient) visits, inpatient stays, and pharmacy claims will be created. Other medical visits are a residual category that includes, but is not limited to, services rendered at independent laboratories, assisted living facilities, and by home health providers. An indicator variable will be created to identify inpatient stays with an acute stay during the inpatient stay, the time to first inpatient stay will also be captured. The time to first inpatient stay, the time to first eD visit during follow-up will be captured.
- COPD and/or pneumonia-related health care resource utilization: This utilization will be calculated analogously to all-cause utilization, but restricted to medical claims with a diagnosis for COPD and/or pneumonia, in any position (Appendix 1) and pharmacy claims for a COPD-related treatment (Appendix 2), including COPD-guideline recommended antibiotics (Appendix 3).

- COPD-related health care resource utilization: This utilization will be calculated analogously to all-cause utilization, but restricted to medical claims with a diagnosis for COPD in any position (Appendix 1) and pharmacy claims for a COPD-related treatment (Appendix 2), including COPD-guideline recommended antibiotics (Appendix 3)
- Pneumonia-related health care resource utilization: This utilization will be calculated analogously to all-cause utilization but restricted to medical claims with a diagnosis for pneumonia in any position (Appendix 1).
- COPD or pneumonia-attributable health care resource utilization: This utilization will be calculated analogously to all-cause utilization, but restricted to medical claims with a diagnosis for COPD or pneumonia in the primary position or a diagnosis for acute respiratory failure in the primary position and a diagnosis for COPD or pneumonia in a non-primary position (Appendix 1) and pharmacy claims for a COPD-related treatment (Appendix 2), including COPD-guideline recommended antibiotics (Appendix 3)
- All-cause health care costs (insurer + patient paid amounts): Health care costs will be computed from the payer and patient perspective together. This is the actual amount paid to the provider by the health plan plus the patient co-pay and/or coinsurance amounts, rather than an estimated cost. Total costs will be calculated and presented as the combined pharmacy costs and medical costs. Medical costs will be presented and will include sub-categories of physician office costs, hospital outpatient costs, emergency services costs, inpatient costs, and other costs.
 - Costs will be adjusted to 2019 dollars using the medical care component of the Consumer Price Index (CPI) to reflect inflation between the date of the claim and 2019.²² The final report will include additional columns with the latest available 2020 mid-year CPI adjustment applied to costs for scaling the results as needed.²²
 - Costs from other payers may be important, particularly for studies involving older patients dually eligible for commercial and Medicare coverage. In consultation with this study will NOT incorporate the amounts estimated to be paid by other payers for a total paid or allowable amount.²³
- COPD and/or pneumonia-related health care costs (insurer + patient paid amounts): These costs will be calculated analogously to the all-cause costs, but restricted to medical diagnosis claims with а for COPD. pneumonia, or acute bronchitis/bronchiolitis in any position (Appendix 1) and pharmacy claims for a COPDrelated treatment (Appendix 2), including COPD-guideline recommended antibiotics (Appendix 3).
- COPD-related health care costs (insurer + patient paid amounts): These costs will be calculated analogously to the all-cause costs, but restricted to medical claims with a diagnosis for COPD in any position (Appendix 1) and pharmacy claims for a COPD-related treatment (Appendix 2), including COPD-guideline recommended antibiotics (Appendix 3).

Proprietary confidential information © 2022 Boehringer Ingelheim International GmbH or one or more of its affiliated companies

- Pneumonia-related health care costs (insurer + patient paid amounts): These costs will be calculated analogously to the all-cause costs but restricted to medical claims with a diagnosis for pneumonia in any position (Appendix 1).
- COPD or pneumonia-attributable health care costs (insurer + patient paid amounts): These costs will be calculated analogously to the all-cause costs, but restricted to medical claims with a diagnosis for COPD or pneumonia in the primary position or a diagnosis for acute respiratory failure in the primary position and a diagnosis for COPD or pneumonia in a non-primary position (Appendix 1) or pharmacy claims for a COPDrelated treatment (Appendix 2), including COPD-guideline recommended antibiotics (Appendix 3).

Clinical characteristics will be measured in the baseline period. The baseline period will include claims occurring on the index date, except for the index medication claims, which will be included in the follow-up period.

- Quan-Charlson comorbidity score: A comorbidity score will be calculated based on the presence of diagnosis codes (in any position) on medical claims in the baseline period. 24.25.26 The score is calculated based on a weighted sum of 12 comorbid conditions. The score represents the cumulative likelihood of one-year mortality and serves as a proxy for comorbidity burden. The Quan-Charlson comorbidity score also will be categorized into the following groups: zero, one, two, three, four, and five or more.
- Oxygen therapy: Evidence of oxygen use will be captured in the baseline period based on diagnosis (ICD-9, ICD-10), procedure (HCPCS, CPT, ICD-9) and revenue codes for oxygen therapy (Appendix 1).
- Baseline respiratory medication utilization: Indicator variables for respiratory medication classes and selected individual respiratory medications will be based on both pharmacy and medical claims (nebulizer treatments may appear in medical claims). Medication classes will include: LAMAs (alone; overall and separately), LABAs (alone), ICS (alone), ICS/LABA single inhaler combination medications, SAMAs (alone), SABAs (alone), SAMA/SABA single inhaler combination medications, any rescue (SAMA alone, SABA alone, or SAMA/SABA single inhaler combination medications), methylxanthines, phosphodiesterase-4 (PDE-4) inhibitors and oral corticosteroids (OCS). Baseline medication use variables will exclude claims which make up the index therapy assignment. Number of fills by class will also be captured. Indicator variables will be created to identify patients who are naïve to long-acting bronchodilators (free or fixed dose LAMAs or LABAs) and to long-acting bronchodilators plus inhaled corticosteroids (free or fixed dose LAMAs, LABAs, and ICSs) at index.
- Index provider specialty: The specialty of the provider on the index prescription fill will be captured. If no provider specialty is recorded on the index prescription fill, the provider specialty from the most recent COPD-related visit on or prior to the index date will be captured. An indicator variable will identify if the provider specialty was determined from the index pharmacy claim. Provider specialty will be classified as one of the following: pulmonology, primary care [family practice, general practice, and

Proprietary confidential information © 2022 Boehringer Ingelheim International GmbH or one or more of its affiliated companies

geriatrics], internal medicine, allied health professional, cardiology, other specialty, and unknown specialty. If claims for more than one provider occur on the date used to classify the provider's specialty, the hierarchy of categories listed above will be used to pick a single provider specialty.

- Pulmonology visits within 30 days of index date: An indicator variable will be created to identify patients with a pulmonologist visit within 30 days prior to and excluding the index date.
- Spirometry testing: If available, indicator and count variables will be created to identify
 patients with lung function testing (Appendix 1). A count of spirometry tests during the
 baseline period will be created. Multiple spirometry tests within a 30-day period will
 be counted as one test.

Patient characteristics will be measured as of the index date, or the first available claim after the index date with valid values for each of the characteristics. It may be necessary to modify or remove some variables or analytic table templates to preclude identification of individual patients and protect proprietary health plan information.

- Index year: The year of the patient's index date will be identified.
- Seasonality: The month of the patient's index date will be identified and classified as fall (September, October, November), winter (December, January, February), spring (March, April, May), or summer (June, July, August).
- Age: Age will be defined as of the index year
- Age groups: Patients will be assigned to one of the following age groups: 40-44, 45-49, 50-54, 55-59, 60-64, 65-69, 70-74, 75-79 and 80+
- Gender: Gender will be captured from enrolment data; patients with undefined gender will be removed from the study sample
- Race/ethnicity: Race/ethnicity information will be captured if available in the database, no further linking with any additional consumer sociodemographic data will be attempted, but if data is available it will be categorized as follows: White, African American/Black, Asian, Hispanic, or unknown (unknown includes missing). This variable depends on the availability of data and will be missing for some or all patients.
- Insurance type: Whether the patient was covered under a commercial or Medicare Advantage health plan will be captured
- Plan type: Plan type will be categorized as Exclusive Provider Organization (EPO), Health Maintenance Organization (HMO), Point of Service (POS), Preferred Provider Organization (PPO), Individual and Other
- Geographic region: The US region in which the study patient is enrolled in a health plan will be determined and reported and states will be categorized into five geographic regions in accordance with the US Census Bureau's region designations; the four health plan regions are presented in the table 1 below. Patients categorized into "other" will be excluded from the study.

Region	State
Northeast	CT, MA, ME, NH, RI, VT, NJ, NY, PA
Midwest	IL, IN, MI, OH, WI, IA, KS, MN, MO, ND, NE, SD
South	DC, DE, FL, GA, MD, NC, SC, VA, WV, AL, KY, MS, TN, AR, LA, OK, TX
West	AZ, CO, ID, MT, NM, NV, UT, WY, AK, CA, HI, OR, WA

Table 1Health Plan Regions

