9.3.2 Outcomes

9.3.2.1 Primary Outcomes

The primary outcome event for effectiveness is time to first COPD exacerbation after cohort entry. The event is defined as follows:

- Severe exacerbation:
 - Hospitalization with a principal discharge diagnosis of COPD and/or
 - An emergency department (ED) visit with a discharge diagnosis of COPD
 - An inpatient admission or an ER visit with a diagnosis code for acute respiratory failure in the primary position and a COPD diagnosis code in any position
- Moderate exacerbation:
 - \circ An antibiotic for a respiratory condition dispensed \pm an OCS

Time to the first COPD exacerbation will be measured from index date until the occurrence of a hospitalization for COPD (severe exacerbation) or ED visit for COPD (severe exacerbation) or prescription of an antibiotic \pm an OCS on the same day (moderate exacerbation). Severe and moderate exacerbations were considered as a composite for main analyses. Sensitivity analyses will include stratification by exacerbation severity.

Exacerbations will be categorized as moderate or severe and a count of any (severe or moderate), severe, and moderate will be provided.

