9.7.1 Main analysis

Analyses will be presented comparing Stiolto vs Trelegy overall after PSM matching and stratified as follows if the sample size allows (at least 15% in each strata):

• Low history of exacerbation: 0 inpatient (i.e., severe exacerbations) and 0-1 outpatient events (i.e., moderate exacerbations)

Proprietary confidential information © 2022 Boehringer Ingelheim International GmbH or one or more of its affiliated companies

• High history of exacerbation: ≥1 inpatient (i.e., severe exacerbations) or ≥2 outpatient events (includes ED)

We will describe the formation of the study cohort. Patient characteristics at baseline in patients treated with Stiolto and patients treated with Trelegy will be assessed separately using standard descriptive statistics.

Propensity scores including both pre-specified and data-derived variables will be then calculated. Balance of patient characteristics between the cohorts will be described before and after propensity score application and compared using standardized differences. For each Stiolto patient, a Trelegy patient with the closest available propensity score will be selected. Nearest neighbor matching method with a caliper of 0.2 will be utilized. Standardized differences greater than 0.10 (10%) will be taken to indicate imbalance, and these variables will also be included in outcome models, categorized as appropriate.

For the analysis of the primary objective, a Cox proportional hazard regression model will be used to perform an as-treated analysis that assesses the effect of first line maintenance medication with Stiolto versus the first line maintenance medication with Trelegy on the time to first COPD exacerbation. This estimates the HR of a COPD exacerbation associated with Stiolto use relative to Trelegy use, along with 95% CI. Based on the days' supply post index date, allowing a grace period of 45 days following the end of days' supply to account for intermittent use.

Stratified analyses will be using the same approach as the main analysis. Calculation of propensity scores will be repeated within the subset of the cohort with available results to create weighted populations suitable for these stratified analyses.

The analysis of the secondary objective related to the risk of pneumonia will also be assessed using Cox proportional hazard regression models with an as-treated approach, like that of the primary analysis.

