APPENDIX 2: COPD-RELATED RESPIRATORY MEDICATIONS AND CLASSES

Drug Class	Subclass	Medication
Maintenance		aclidinium
medications	Inhaled long-acting anti-	glycopyrrolate
	muscarinic	revefenacin
	agents (LAMA)	tiotropium
		umeclidinium
		arformoterol
	Long-acting β-agonists (LABA)	formoterol
		indacaterol
		olodaterol
		salmeterol
		beclomethasone
		budesonide (both inhaler and nebulizer)
	Inhaled corticosteroids (ICS)	ciclensonide
		flunisolide
		fluticasone
		mometasone
		triamcinolone

Boehringer Ingelheim Non-Interventional Study (NIS) Protocol BI Study Number 1237-0121

c38026921-01

Proprietary confidential information © 2022 Boehringer Ingelheim International GmbH or one or more of its affiliated companies

Drug Class	Subclass	Medication	
		aclidinium/formoterol	
	Inholod I AMA/I ADA	glycopyrrolate/formoterol	
	innaled LAMA/LABA	indacaterol/glycopyrrolate	
	combination	tiotropium/olodaterol	
		umeclidinium/vilanterol	
		budesonide/formoterol	
	Inhaled ICS/LABA	fluticasone/salmeterol	
	combination	fluticasone/vilanterol	
		mometasone/formoterol	
	Inholod ICS/LADA/LAMA	Budesonide/glycopyrrolate/formoterol	
	initiated ICS/LABA/LAWA	fumarate ¹	
	combination	Fluticasone/umeclidinium/vilanterol	
	Mathulyanthing	aminophylline	
	(intravenous oral)	dyphylline	
	(intravenous, orar)	theophylline	
	PDE-4 inhibitor (oral)	roflumilast	
Rescue		albuterol	
medications		bitolterol	
	Short-acting B-agonists	isoetharine	
	(SABA) (inhalation oral)	isoproterenol	
		levalbuterol	
		metaproterenol	
		pirbuterol	
	Short-acting anti-muscarinic	ipratropium	
	Agents (SAMA) (inhalation)		
	SAMA/SABA (inhalation)	ipratropium/albuterol	
		betamethasone	
		dexamethasone	
	Oral corticosteroids $(OCS)^2$	hydrocortisone	
		methylprednisolone	
		prednisolone	
		prednisone	

¹This medication was FDA approved for maintenance treatment of COPD on 24 July 2020, which is outside of the study time period, and will not be included in this study.

²Including tablets, oral solutions, elixirs, etc. Injectable corticosteroid medications will not be included.

Proprietary confidential information © 2022 Boehringer Ingelheim International GmbH or one or more of its affiliated companies

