APPENDIX 3: COPD GUIDELINE-RECOMMEND ANTIBIOTIC MEDICATIONS

Drug Category	Drug Class	Medication	
COPD Guideline-		cefaclor	
recommended Antibiotics ¹		cefdinir	
		cefditoren	
		cefepime	
	Cephalosporins	cefpodoxime	
		cefprozil	
		ceftibuten	
		ceftriaxone	
		cefuroxime	
	M	azithromycin	
	Wacrondes	clarithromycin	
		amoxicillin	
	Penicillins	amoxicillin/potassium	
		piperacillin/tazobactam	
		levofloxacin	
	Quinoiones	moxifloxacin	
	Sulfonamide	sulfamethoxazole/trimethoprim	
	combinations		
	Tetracyclines	doxycycline	

¹The American Thoracic Society (2017) and Global Initiative for Chronic Obstructive Lung Disease (2020) guidelines recommend that antibiotics for acute exacerbation of chronic bronchitis be selected based on local sensitivity patterns. For more specific recommendations, The Sanford Guide to Antimicrobial Therapy (2020) was referenced.

COPD Exacerbation Definition

- **Exacerbation Hierarchy:** Exacerbation events will be classified as severe or moderate according to the highest severity contributing event.
- **Exacerbation Episodes:** Exacerbations occurring within 14 days of each other will be considered a single exacerbation episode and will be classified according to the highest severity contributing event.
- Episode Length: The start date of the exacerbation episode will be the service date of the first event (medical encounter or pharmacy fill for an OCS or antibiotic). The end date of the exacerbation episode will be defined as the last observed exacerbation event date (or discharge date if an inpatient event) + 14 days.

Proprietary confidential information © 2022 Boehringer Ingelheim International GmbH or one or more of its affiliated companies

• Single Event Episode

- In a single event episode, the exacerbation begins with the earliest occurrence of these events: COPD exacerbation defined inpatient admission, ER visit, ambulatory visit, or corticosteroid or antibiotic dispensing as defined in Section 9.3.2.1. In a single event episode, the exacerbation ends 14 days from the start of the event, hospital discharge, or following the OCS or antibiotic dispensing, whichever is later.
- *Episode Start date* = service date of a qualifying event (inpatient admission, ED visit, ambulatory visit, or OCS or antibiotic dispensing).
 - If the qualifying event is a hospitalization, the start date is the admission date.
 - If the qualifying event is an ED visit, the start date is the service date.

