 - If the qualifying event is an ambulatory visit or an OCS or antibiotic dispensing, the start date is the earliest of the associated medical visit or medication dispensing date.

Episode End Date

- \circ If the qualifying event is a hospitalization: discharge date + 14 days
- \circ If the qualifying event is an ER visit: start date + 14 days
- If the qualifying event is an ambulatory visit or an OCS or antibiotic dispensing: Fthe latest of the medical visit or medication dispensing + 14 days
- If the Episode End Date is after the end of follow-up, then set an additional flag CENSORED=1.
- NOTE: Under this definition, it is possible for the runout of a medication to exceed the End Date.
- MULTIPLE EVENT EPISODES
- If another qualifying event occurs before the episode End Date, then the episode is extended. The date of the second event is used to reset the End Date per the definition above, using information from this second event. The process continues until a 14-day period with no exacerbation qualifying events occur. The End Date is set (as defined above).
- *Episode Length:* (End date Start date) + 1

Proprietary confidential information © 2022 Boehringer Ingelheim International GmbH or one or more of its affiliated companies

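### The moderate-exacerbation rule has no days'-supply or new-course condition, so refills of long-term oral corticosteroids or antibiotics near a COPD-coded visit count as new exacerbations

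*Combined protocol and SAP*

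**What the plan says.** Section 9.3 gives three routes to a moderate exacerbation. Each needs an ambulatory visit with COPD coded anywhere on the claim. The first adds "a pharmacy claim for an oral corticosteroid (OCS) prescription within ±7 days of the office/outpatient visit", the second adds "a pharmacy claim for respiratory antibiotic prescription within ±7 days of the office/outpatient visit", and the third asks for both drugs.

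The drug lists restrict by agent and formulation only. The oral corticosteroid (OCS) list in Appendix 2 includes prednisone and "hydrocortisone", and its one restriction on claims is "Injectable corticosteroid medications will not be included". The antibiotic list in Appendix 3 includes "azithromycin". Days' supply is used for the index inhaler (9.3.1, 9.7.1) but nowhere for the outcome drugs.

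Under the episode rules in Appendix 3, an episode starts at the earlier of the visit and the fill and ends 14 days after the later one. Further events before that end date are merged. The appendix adds that "Under this definition, it is possible for the runout of a medication to exceed the End Date", and gives no rule for that case.

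Two other texts define the same event:
- Section 9.3.2.1 (Primary Outcomes) has "An antibiotic for a respiratory condition dispensed", with or without OCS. No visit is needed, and OCS alone is not listed.
- Sections 9.1 and 9.2.2 have an antibiotic, with or without OCS, within 7 days of a visit, and refer to the primary diagnosis rather than any position.

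Exacerbations feed two primary objectives (time to first event, and comparison of exacerbations, with counts promised in 9.3.2.1). They also feed the baseline covariate 0, 1 or ≥2 in the propensity score (9.3.3) and the Low/High history strata (9.7.1), where two outpatient events are enough for High. No separate definition is given for baseline history, so I assume the same rule applies there.

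**The concern.** A claims definition of a moderate exacerbation uses the drug claim as a marker of acute treatment. That works only if the claim starts an acute course. A patient on continuing prednisone for another disease, on hydrocortisone replacement or on long-term azithromycin refills whether or not anything has happened to the lungs. If a visit that happens to list COPD falls within a week of the refill, section 9.3 records an exacerbation.

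Such events are not expected to respond to either inhaler. In the outcome they dilute the comparison. That matters in a study where a hazard ratio near 1 may be read as similar effectiveness of the two products. In the baseline year they can move a stable patient into the ≥2 category of the propensity score and into the High stratum.

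**Working it through.** **The plan's own figure.** The only related figure is power of at least 80% with 3018 patients per matched group (9.5). No alpha, target hazard ratio or event rate is given, so it cannot be reproduced, and this point does not depend on it.

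**1. Can the 14-day rule merge monthly refills?** Put fills on day 0 and day 30.
- Latest end of the first episode: visit on day 7, plus 14 days = day 21.
- Earliest start of the next: visit on day 30 − 7 = day 23.

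Day 23 is after day 21, so episodes around successive 30-day fills never merge. Longer supplies leave wider gaps.

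**2. Upper limit under section 9.3.** With a COPD-coded visit beside every fill over 365 days, applying the rule gives 13 episodes for 30-day fills, 7 for 60-day fills and 5 for 90-day fills. Fills every 14 days merge into one.

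**3. Randomly timed visits under section 9.3.** The ±7-day window covers 15 days. Assume four COPD-coded visits a year and a full year on treatment.

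| Fill length | Chance per visit | Events per year before merging | At least one in the year |
|---|---|---|---|
| 30 days | 15/30 = 0.50 | 4 × 0.50 = 2.0 | 1 − 0.50^4 = 94% |
| 90 days | 15/90 = 0.17 | 4 × 15/90 = 0.67 | 1 − (75/90)^4 = 52% |

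Simulating the full rule for 30-day fills, which merges visits that share a fill, gives a mean of 1.87 episodes a year, with 66% of such patients reaching two or more. With 2, 6 or 12 visits a year the means are 0.96, 2.68 and 4.78.

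**4. Section 9.3.2.1 instead.** No visit is needed, so 30-day azithromycin fills give 13 episodes a year. OCS-only refills give 0.

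**5. Effect on the hazard ratio.** Let f be the share of the reference group's events that are refills unrelated to treatment, equally frequent in both groups. Then observed HR = (1 − f) × true HR + f. For illustration, take a true HR of 0.83 (a subgroup value quoted in 9.5), 1000 events, and two-sided alpha 0.05. The event number, the alpha and f are all assumptions.

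| f | Observed HR | Power |
|---|---|---|
| 0 | 0.83 | 84% |
| 5% | 0.839 | 80% |
| 10% | 0.847 | 75% |
| 20% | 0.864 | 64% |

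If 30% to 50% of patients have an event (also an assumption), f = 20% requires a false first event in 0.2 × 30% = 6% to 0.2 × 50% = 10% of the cohort.

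**The case against.** The strongest reply is that the problem may be small and is partly contained.

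- **Population.** Section 9.2.2 excludes patients with two claims for asthma, interstitial lung disease, cystic fibrosis or lung cancer, and anyone on inhaled maintenance therapy in the previous six months. This probably removes some long-term users. It does not remove those treated for other conditions, or all users of prophylactic antibiotics.
- **Confounding control.** OCS and antibiotic use are propensity covariates (9.3.3), fill counts by class, including OCS, are captured (9.3), and data-derived variables may enter the score (9.7.1). Matching on prior exacerbations would also tend to balance long-term users. This stands as an argument against a difference between groups. It does not remove the false events or the dilution.
- **Severe events.** Section 9.3.2.1 promises stratification by severity. Severe events need no drug claim, so that analysis does not take on these false events. The main composite does.
- **Follow-up.** Patients are censored at discontinuation or switch, so many have less than the full year assumed above.
- **General caveats.** Section 9.9 acknowledges outcome misclassification and promises bias analysis as appropriate, but specifies none for this error.
- **Governing definition.** If 9.3.2.1, 9.1 or 9.2.2 governs, refills of OCS alone are not events. This is correct, and it makes the OCS part conditional.

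**Conclusion.** The gap is real: no text separates a new acute course from continuing supply, and the merge rule cannot do so for monthly or longer fills. Under section 9.3, a long-term user with four randomly timed COPD-coded visits in a full year on treatment has about 2 false episodes with 30-day fills and about 0.7 with 90-day fills. The first can enter time to first exacerbation. Repeats affect the counts, the 0/1/≥2 covariate and the Low/High strata. The likely result is non-differential misclassification that pulls the hazard ratio towards 1. How far cannot be computed, because the documents give no prevalence of long-term use; the values of f above are illustrations.

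A reader might infer more than the documents support:
- That every refill opens an episode. Under 9.3 only refills within 7 days of a COPD-coded visit count; only the antibiotic text in 9.3.2.1 drops the visit.
- That repeated refills distort the Cox analysis. It uses the first event only.
- That long-term users are channelled to triple therapy and bias the comparison by group. This is possible but not shown, and the matching may limit it.
- That the run-out note in Appendix 3 shows long-term refills were foreseen. It shows only that one supply can outlast an episode.

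**What to change.** First reconcile the moderate definition across 9.1, 9.2.2, 9.3 and 9.3.2.1, since this decides whether OCS alone counts and whether a visit is needed. Then:

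1. State in 9.3, 9.3.2.1 and Appendix 3 that an OCS or antibiotic claim qualifies only if it starts a new short course: a ceiling on days' supply, and no overlapping or recent supply of the same class. Values such as at most 21 days' supply and none in the preceding 14 days would serve as examples; the sponsor should set and justify the cut-offs.
2. Apply the same rule to baseline exacerbation history and to the Low/High strata.
3. Add a baseline long-term-use flag (for example at least 90 cumulative days' supply in the 12-month baseline) to the propensity score.
4. Run one sensitivity analysis excluding long-term users, and report how many there are in each group.

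The cost is protocol wording and programming; days' supply is already used to define exposure. The drawback is that any cut-off is a convention, and some true bursts in long-term users, or long tapers, will be missed.
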